10.3.3 Analysis of AEs for Intermittent Treatment

The following analyses will be performed for the Intermittent Treatment:

- 1. Rates (event per 100 patient-years of exposure to HUMIRA®) of treatment-emergent SAEs, AEs of Special Interest and AEs that lead to permanent discontinuation of HUMIRA® and the 95% confidence interval will be provided.
- 2. Rates (event per 100 patient-years) of SAEs, AEs of Special Interest and AEs that lead to permanent discontinuation of HUMIRA® and the 95% confidence interval over the course of intermittent treatment strategy, defined as from the first day of HUMIRA® injection to the end of the last treatment period, will be provided.

To further evaluate the effect of intermittent treatment on the AE profile, rates of AEs per 100 patients-years of exposure to HUMIRA® will be analyzed for each treatment period for the subgroups of patients with at least 3, 4, and 5 or more TIs.

	Overall	1 st Treatment Period	2 nd Treatment Period	3 rd Treatment Period	4 th Treatment Period	5 th Treatment Period	6 th + Treatment Period
> 2 TIs ^a	X.XX	X.XX	X.XX	x.xx			
> 3 TIs	X.XX	X.XX	X.XX	x.xx	X.XX		
> 4 TIs	X.XX	X.XX	X.XX	x.xx	x.xx	X.XX	
> 5 TIs	X.XX	X.XX	X.XX	x.xx	x.xx	X.XX	X.XX

a. This is the Intermittent Treatment Population.

Summaries of AEs among patients not in the Intermittent Treatment Population will be provided as a reference.

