7.4 Adverse Event Collection Period

SAEs, AEs of Special Interest, and AEs that lead to permanent registry HUMIRA[®] discontinuation will be reported to AbbVie starting from the first commercial dose of HUMIRA[®] or when the initial informed consent is signed, (whichever date is earlier), throughout the patient's participation in the registry, or direct to HCP process, until satisfactory resolution or for 70 days after their last dose of registry drug (whichever period is longer) to further evaluate safety.

Follow-up received on ongoing SAEs and/or AESIs post registry conclusion should be reported using standard Post-Marketing Reporting.

[figure not shown]
For patients participating in the direct to HCP process, surgeries, hospitalizations, deaths, events listed as AEs of Special Interest (Table 2), and AEs of Special Interest that lead to permanent discontinuation of HUMIRA® will be collected.

In the event HUMIRA[®] therapy is interrupted (Section 10.1), the patient will remain in the registry and continue to be monitored during the treatment interruption for SAEs and AEs of Special Interest and will be questioned for changes in their psoriasis medications and medical history of the event at their registry visits. If treatment with HUMIRA[®] is permanently discontinued for any reason, the reason will be recorded and the patient should be encouraged to remain in the registry for the full 10 years.

For patients enrolled from a prior AbbVie HUMIRA® study, ongoing events at the time of registry entry will be collected.

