10.0 Data Analysis Plan

10.1 Analyzable Populations

All Treated Patient Population is defined as patients who receive at least one dose of HUMIRA® in the registry.

New Prescription Patient Population is defined as patients who have newly initiated HUMIRA[®] therapy within 4 weeks prior to the entry into the registry and who receive at least one dose of HUMIRA[®] in the registry (the New Prescription Population is a subset of the All Treated Patient Population).

The All Treated Patient Population and the New Prescription Patient Population will be used for safety and effectiveness analysis.

In addition, the Intermittent Treatment Population, defined as patients who have at least 2 treatment interruption periods with at least 3 treatment periods (Figure 1), will be used for the safety analysis. A treatment interruption period is defined as greater than 70 consecutive days during which the patient does not receive any HUMIRA® treatment. The treatment interruption period starts from 71 days after the last dose of HUMIRA® in

the preceding treatment period and up to the day prior to the first dose of $HUMIRA^{@}$ in the subsequent period. A treatment period is defined as at least one dose of $HUMIRA^{@}$ up to 70 days after the last dose of $HUMIRA^{@}$.

Last Dose First Dose First Dose Day 70 Post-TI (#1) Pre-TI (#1) On Drug Off Drug = TI Drug On 70 days after last dose Treatment Period 1 -Treatment Interruption 1 -**Treatment Period** through 70 days after last dose Begins Day 71 after last dose 2, 3....N

[figure not shown]
Figure 1. Treatment Period and Treatment Interruption (TI) Period

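### The intermittent-strategy rate in 10.3.3 item 2 stops 70 days after the final dose, so it is biased low for deaths and for events that prevent a restart

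*Protocol*

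**What the plan says.** Section 10.3.3 of the Protocol plans two overall rates for the Intermittent Treatment Population. Item 1 uses patient-years of drug exposure. Item 2 gives rates of SAEs, AEs of Special Interest and AEs leading to permanent discontinuation, "and the 95% confidence interval over the course of intermittent treatment strategy". Its window is "defined as from the first day of HUMIRA® injection to the end of the last treatment period".

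The terms come from section 10.1:
- A treatment period runs from its first dose to 70 days after its last dose.
- On interruptions: "A treatment interruption period is defined as greater than 70 consecutive days during which the patient does not receive any" drug. An interruption starts on day 71 after the last dose in "the preceding treatment period and up to the day prior to the first dose of" drug in the next period.
- The population is "patients who have at least 2 treatment interruption periods with at least 3 treatment periods".

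Section 7.4 says that patients whose therapy is interrupted stay in the registry and "continue to be monitored during the treatment interruption for SAEs and AEs of Special Interest". Patients who stop for good are encouraged to remain for the full 10 years.

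**The concern.** A rate for an on/off strategy should count off-drug time and the events in it by the same rule. Here, an off-drug interval beyond day 70 enters item 2 only if a later dose closes it. A patient who dies in such an interval, or has an event there that rules out restarting, contributes neither the event nor the time from day 71. A patient who comes through the interval and restarts contributes all of its time. Inclusion thus depends on the outcome.

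Item 2 is the only planned rate for this population that is meant to include off-drug time. Item 1 and the per-period table use drug exposure. The analysis to last contact in 10.3.1 is specified for the All Treated Patient Population, and 10.3.5 extends it to the New Prescription Patient Population. Section 10.3.4 does not name the intermittent group. Summaries for patients outside the population are to be given as a reference, so a low death rate in item 2 could be read as reassurance about intermittent use.

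**Working it through.** The Protocol gives no figure for the item 2 rate, so there is none to reproduce. The check has two parts: what follows from the definitions, and an illustration of size.

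**1. From the definitions (10.1 and 10.3.3)**
- End of window = end of last treatment period = final dose + 70 days.
- Each counted interruption ends the day before a next first dose, so the patient was alive and restarted.
- Counted interruptions therefore contain no deaths and no events that prevented restart, yet all their days are in the denominator.
- Events up to day 70 after the final dose are counted. The loss begins on day 71.

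**2. General expression**

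Let d be the share of events, and p the share of patient-years, that fall after the window. Then

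rate as written / rate to last contact = (1 − d) / (1 − p).

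The rule does little harm when d ≈ p and biases the rate low when d > p.

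**3. Simulation with no permanent stops**

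Assumed: 2.0 per 100 PY on and off drug for an event that ends treatment; 10 years; on-drug spells of mean 12 months plus 70 days; at least 3 treatment periods; counting from first injection, as item 2 does.

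| Mean off-drug interval | As written | To last contact | Ratio |
|---|---|---|---|
| 3 months | 1.19 | 1.43 | 0.83 |
| 6 months | 0.96 | 1.31 | 0.73 |
| 12 months | 0.71 | 1.13 | 0.63 |

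The end rule alone lowers the rate by 17%, 27% and 37%. Between 17% and 39% of these events fall after the window.

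**4. Simulation with permanent stops**

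Assumed: 1.0 per 100 PY; 10 years; on-drug mean 1 year; off-drug 70 days plus mean 0.75 years; a 60%, 80% or 95% chance of planning a restart after each stop; 60,000 patients per scenario; at least 3 treatment periods.

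Deaths, 80% chance:
- As written: 1,094 / 290,464 PY = 0.38 per 100 PY.
- To last contact: (1,094 + 1,088) / (290,464 + 70,030) = 2,182 / 360,494 = 0.61 per 100 PY.
- d = 1,088 / 2,182 = 50%; p = 70,030 / 360,494 = 19%.
- Ratio = 0.501 / 0.806 = 0.62, so 38% lower.

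For deaths at 60%, 80% and 95%, the rates as written are 0.36, 0.38 and 0.42, against 0.64, 0.61 and 0.62 to last contact. The end rule lowers the rate by 43%, 38% and 33%, and drops 61%, 50% and 38% of deaths. Cancers that stop further treatment behave alike (0.34 to 0.40, against about 0.62).

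Cancers that do not affect restart, 80% chance:
- As written: 2,872 / 293,594 PY = 0.98 per 100 PY.
- To last contact: (2,872 + 741) / (293,594 + 69,634) = 3,613 / 363,228 = 0.99 per 100 PY.
- d = 741 / 3,613 = 21%; p = 69,634 / 363,228 = 19%. Almost no bias.

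**5. What the end rule does not explain**

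In step 4 at 80%, moving the end takes the death rate from 0.38 to 0.61, not to 1.0. If the clock also starts at the third treatment period, it is 0.99. The rest is time before the third period, which every member of the population must have survived.

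**The case against.** - **Estimand.** A patient who has stopped for good has left the strategy and may spend years on other therapy, so ending at the last treatment period can be defended. This stands in part: a total to last contact mixes in that time. But a patient who dies off drug cannot be told apart from one who had stopped permanently, and the rule settles the matter by outcome. Showing the time separately serves both readings.
- **The events are not lost.** A reader might infer that they vanish from the registry's results. They do not. Section 10.3.1 counts them to last contact for all treated patients, and 10.3.4 counts those outside the HCP process. The fault is confined to one descriptive rate in one subgroup.
- **Direction.** A reader might infer that item 2 is too low for every event. The definitions do not support that: step 4 shows almost no bias when the event does not affect restart. Worsening of psoriasis, an AE of Special Interest in Table 2, may prompt restart and could be overstated.
- **Cancers.** A reader might also infer that any malignancy bars restart. Section 3.0 urges only caution in such patients, and Table 2 includes non-melanoma skin cancer. The point applies to a cancer only if it keeps the patient from restarting.
- **Last contact is not a clean end.** As defined in 10.3.1 it includes the HCP process. Section 6.5 places SAEs outside that questionnaire beyond the protocol's requirements. Adding HCP time to an SAE denominator would create a new downward bias. This stands, and the fix allows for it.

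**Conclusion.** The concern holds in a limited form. By the Protocol's own definitions, the item 2 rate includes off-drug time beyond day 70 only when the patient restarts, and drops events from day 71 after the final dose. It is therefore biased low for deaths and for events that prevent a restart.

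The direction follows from the definitions if the hazard is constant. The size does not, because spell lengths, restart chances and event rates are assumed. Over the inputs tried, the end rule lowers these rates by 17% to 37% without permanent stops and by 33% to 43% for deaths with them.

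A reader might infer that moving the end of the window recovers the true rate. It does not: in the first illustration the rate rises only to 1.43, 1.31 and 1.13 against a true 2.0. The remainder comes from requiring at least three treatment periods, which is a separate issue.

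**What to change.** In 10.3.3 item 2, for the Intermittent Treatment Population:

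1. Run the window from first injection to death or last registry contact excluding the HCP process, as in 10.3.4. Add HCP-process time only for deaths and AEs of Special Interest, which are collected there.
2. Keep the rate to the end of the last treatment period, and report events and patient-years after that point on a separate line beside it.

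The cost is a short change of text in 10.3.3 or the SAP and one extra table line. No new data are needed, because off-drug follow-up is already planned in 7.4. The downside is that the total includes some time after permanent discontinuation, possibly on other therapy; the separate line makes that visible. The survivorship built into the three-period entry rule is not cured by this change and should be stated as a limitation of the rate.

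### Section 10.3.3: the reference group mixes patients with no interruption and patients re-treated once, and the by-period table shows the first re-treatment only for patients who reached a third treatment period

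*Protocol*

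**What the plan says.** Protocol Section 10.1 sets up the Intermittent Treatment Population, "defined as patients who have at least 2 treatment interruption periods with at least 3 treatment periods". On interruptions it says: "A treatment interruption period is defined as greater than 70 consecutive days during which the patient does not receive any HUMIRA® treatment". An interruption runs from 71 days after the last dose in "the preceding treatment period and up to the day prior to the first dose of" the drug in the next period, so a completed interruption always ends in a restart.

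Section 10.3.3 gives overall rates for this population and then adds a by-period analysis, introduced with the aim "To further evaluate the effect of intermittent treatment on the AE profile". Rates per 100 patient-years of exposure "will be analyzed for each treatment period for the subgroups of patients with at least 3, 4, and 5 or more TIs". The first row of the table shell carries the footnote "a. This is the Intermittent Treatment Population", and no row sits below it. The section closes with the reference: "Summaries of AEs among patients not in the Intermittent Treatment Population will be provided as a reference". Nothing in Sections 10.1 to 10.3.5 divides that reference by number of interruptions.

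**The concern.** The section asks what stopping and restarting does to the AE profile. A patient with one interruption has done exactly that, once, yet sits in the reference. If re-treatment raises event rates, these patients raise the reference rate and make the intermittent group look closer to it. For a registry whose primary objective is long-term safety (Section 5.0), that is the unfavourable direction.

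The by-period table has a related gap. The first re-treatment is the earliest point at which a restart effect could appear, and the table shows it only for patients who later interrupted and restarted again. A patient whose first re-treatment ended in a permanent stop because of an AE cannot be in any row. Events leading to permanent discontinuation are one of the three event classes the section analyses.

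**Working it through.** The protocol states no figure on this point, so there is none to reproduce. The check is set logic, followed by illustrations on assumed inputs.

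**1. Where each patient falls (definitions in 10.1, reference and table in 10.3.3)**

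| Course | TIs | Treatment periods | Placed in | Row in by-period table |
|---|---|---|---|---|
| No restart after a gap of more than 70 days: still on treatment, or stopped for good in the first period | 0 | 1 | Reference | None |
| One gap, one restart | 1 | 2 | Reference | None |
| Two or more gaps, each followed by a restart | 2 or more | 3 or more | Intermittent Treatment Population | Yes |

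The reference is therefore the 0-TI and 1-TI patients together. Period 2 is tabulated only for patients with a period 3.

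**2. Permanent discontinuation in the existing rows**

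A patient with a third period restarted after periods 1 and 2, so neither ended in a permanent stop. This assumes that a stop followed by a restart is not still coded as permanent. The zero follows from who is in the row and says nothing about the drug.

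Illustration, all inputs assumed: 5% risk per period of an AE leading to permanent discontinuation, the same in every period, and a 40% chance that a re-treated patient without such an event interrupts and restarts again.

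- Re-treated patients who reach a third period: 0.95 × 0.40 = 0.38.
- Re-treated patients with exactly one TI: 1 − 0.38 = 0.62.
- Second-period risk in the Intermittent Treatment Population: 0%.
- Second-period risk in exactly-one-TI patients: 0.05 / 0.62 = 8.1%.
- Second-period risk in all re-treated patients: 5.0%, the true value.

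A simulation under these assumptions, with a 20% chance of a first interruption and restart, gave the same three figures. Only the group with at least one TI recovers the true risk.

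**3. Pull on the reference**

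Let RR be the rate ratio on re-treatment time against first-period time, and p the share of reference patient-years that is re-treatment time. Assume two thirds of the intermittent group's time is re-treatment. Then

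observed ratio = (1/3 + 2/3 × RR) / (1 + p × (RR − 1)).

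| Assumed RR | No re-treatment time in reference | p = 2% | p = 10% | p = 30% |
|---|---|---|---|---|
| 1.5 | 1.33 | 1.32 | 1.27 | 1.16 |
| 2.0 | 1.67 | 1.63 | 1.52 | 1.28 |

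For example, with RR 1.5 and p = 10%: 1.333 / 1.05 = 1.27. The direction is fixed whenever RR exceeds 1. The size depends on p, which the protocol does not give.

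**4. Share of re-treated patients with exactly one TI**

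This share is 1 − q, where q is the chance that a once-re-treated patient interrupts and restarts again. For q = 0.2, 0.4, 0.5 and 0.7 it is 80%, 60%, 50% and 30%. The protocol does not fix q.

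**The case against.** No formal contrast is planned. Section 10.3.3 promises descriptive summaries as a reference, without a ratio, test or hypothesis. Defining intermittent treatment by repeated cycling is a defensible choice: Section 6.5 allows interruption for any reason, and Section 7.6 foresees it in pregnancy, so a single gap need not reflect an intermittent strategy. The statistical analysis plan, not shown, could subdivide the reference. All of this stands. It limits the point to an improvement in presentation; the protocol text still fixes the population, reference and table shell without the split.

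A reader might infer that re-treatment after a single interruption goes unexamined. It does not: those events are counted in the observational and treatment-emergent analyses (10.3.1, 10.3.2, 10.3.4) and in the reference summary. What is missing is a separate or by-period rate.

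A reader might also infer that the overlapping rows, each containing the later ones, are an error, and ask for rows with exactly 1, 2, 3 TIs and so on. Each existing row is one cohort read across its periods, and no row-to-row comparison is planned. Rows for an exact count condition on not restarting again, which piles permanent stops into the last period: the 8.1% against 5.0% above. They would exchange one selection effect for another.

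**Conclusion.** The point holds as a low-cost improvement. Two things follow from the definitions alone: the reference mixes 0-TI and 1-TI patients, and the first re-treatment period is tabulated only for patients who went on to a third. The zero for AEs leading to permanent discontinuation in periods 1 and 2 of those rows also follows, given consistent coding of permanent stops.

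The amount of dilution is not established. It could be trivial or material depending on p, and every ratio above is an illustration. Giving one-TI patients the full effect over all their time would overstate it, because their first treatment period precedes any restart. Nor do the documents show that most re-treated patients fall outside the table; that needs q below 0.5. Calling the reference invalid would also go too far: it is a descriptive summary of a mixed group.

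**What to change.** In Section 10.3.3:

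- Present the reference summary separately for patients with 0 TIs and with exactly 1 TI, counting only interruptions that ended in a restart.
- State that the 0-TI group includes patients who stopped permanently in their first period, and do not label it continuous.
- Add a cumulative row for at least 1 TI, with rates for treatment periods 1 and 2. Its period 2 gives a first re-treatment rate not conditioned on a later restart. Keep the existing cumulative rows.
- Footnote the table: AEs leading to permanent discontinuation are zero by construction in every period that all patients in a row went on to restart after. That is period 1 of the new row, and periods 1 and 2 of the Intermittent Treatment Population row.

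The cost is a few more table cells. TI counts are already needed to define the population, so no new data are collected. Some selection between the 0-TI and 1-TI groups remains, since patients who restart differ from those who do not, and the exactly-1-TI summary still conditions on no second restart. The split should therefore be read descriptively.

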10.3.4 Analysis of Observational AEs Excluding HCP Process

The analysis will be performed using data from first day in the registry through the last contact, excluding the HCP process. The number and percentage of patients experiencing SAEs, AEs of Special Interest and AEs that lead to permanent discontinuation of HUMIRA® will be tabulated by body system and Medical Dictionary for Drug Regulatory Activities (MedDRA®) preferred term. Rates (event per 100 patient-year of observation) of SAEs, AEs of Special Interest and AEs that lead to permanent discontinuation of HUMIRA® and the 95% confidence interval will be provided.

Summaries of SAEs, AEs of Special Interest and AEs that lead to permanent discontinuation of HUMIRA® by severity and relationship to HUMIRA® will be provided.

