6.4 Registry Duration

The planned follow-up observation period is 10 years.

A patient may withdraw from the registry at any time without prejudice. If the physician, for any reason, decides it is in the best interest of the patient to discontinue HUMIRA®, treatment should be stopped. Physicians are encouraged to keep patients in the registry for a full 10-year observation period irrespective of future treatment decisions so that important and complete safety information can be obtained. Patients who develop an AESI or SAE while in the registry will be followed throughout the patient's participation in the registry or direct to HCP process until satisfactory resolution or until 70 days following the last registry dose (whichever is longer). Follow-up received on ongoing SAEs and/or AESIs at the time of registry conclusion should be reported using post-marketing reporting requirements. If a patient withdraws or is withdrawn from the registry, such should be noted, along with the reason for withdrawal on the electronic Study Completion eCRF). At the time of withdrawal, an assessment of the patient's current medical condition will be completed.

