7.1.2 Adverse Events of Special Interest

Table 2. AEs of Special Interest for This Registry

Serious and non-serious opportunistic infections, including the following bacterial, fungal, viral and parasitic infections: Aspergillus, Blastomyces, Candida, Coccidioides, Cryptococcal, Cytomegalovirus, Histoplasma, Listeria, Nocardia, Paracoccidioides, Pneumocystis, Toxoplasma, Tuberculosis, Herpes, Bacillary angiomatosis, Mucormycosis, Progressive Vaccinia, Zygomycosis, BK virus, and JC virus

L	y	m	ıp	h	O.	m	ıa

Hepatosplenic T-cell lymphoma

Leukemia

Non-melanoma skin cancer (NMSC)

Other malignancies (except lymphoma, leukemia and NMSC)

Immune reactions including lupus, lupus-like reactions, and severe allergic reactions

Congestive heart failure (CHF)

Cerebrovascular accident (CVA)

Myocardial infarction (MI)

CNS demyelinating disorders (including MS and Guillain-Barré syndrome)

Hepatic events that are serious or lead to permanent discontinuation of HUMIRA (e.g., persistent liver function test abnormalities, acute liver failure and other serious hepatic events)

Hematologic events that are serious or lead to permanent discontinuation of HUMIRA (e.g., aplastic anemia, Granulocytopenia, Granulocyte Maturation Arrest, Leukopenia, Neutropenia, Pancytopenia and Thrombocytopenia)

Worsening of Psoriasis

Vasculitis

Diverticulitis

Intestinal perforation

In addition, to the SAEs and AEs of Special Interest (Table 2), AEs that lead to permanent discontinuation of HUMIRA® will be collected.

Psoriasis HUMIRA® Registry

For patients participating in the direct to HCP process in addition to surgeries, hospitalizations, deaths, and the events listed as AEs of Special Interest (Table 2), AEs of Special Interest that lead to permanent discontinuation of HUMIRA® will be collected.

During the course of the registry, additional AEs of Special Interest may be identified by AbbVie. Updates to the AEs of Special Interest will be maintained and collected through the eCRF system. Sites will be trained on all updates to the eCRF system.

The physician will assess and record any additional information on the AEs of Special Interest in detail on the AE of Special Interest eCRF.

The physician will assess all reported AEs for seriousness and follow the requirements/timelines for reporting any AE that fulfills the criteria of an SAE, as defined in Section 7.1.3.

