10.2 Demographics and Registry Enrollment Characteristics

Demographics and baseline characteristics will be summarized for the All Treated Patient Population, the New Prescription Patient Population, and the Intermittent Treatment Population. Descriptive statistics will be presented. Number of patients with non-missing values, mean, and standard deviation will be provided for continuous variables. Counts and percentages will be provided for categorical variables. The number and percentage of patients that discontinue from the registry will be summarized, overall and by reason for discontinuation. Duration of observation in the registry and total duration of treatment will be summarized as follows:

Duration of observation in the registry is defined from the first day in the registry (enrollment visit or date of informed consent, up to the end-of-registry (as defined in Section 12.0).

The duration of treatment in the registry (registry exposure) is defined from the first dose of HUMIRA® in the registry to 14 days after the last dose of HUMIRA® excluding total days of any treatment interruptions.

Total duration of treatment (total exposure) is defined from the first recorded dose of HUMIRA® (initial dose) to 14 days after the last dose of HUMIRA® excluding total days of any treatment interruptions.

Time to observational and treatment discontinuation will also be presented as Kaplan-Meier (KM) curves.

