10.3 Safety Analyses

[figure not shown]
Five main safety analyses will be reported from this registry: four analyses will summarize data through the end-of-registry (as defined in Section 12.0) and one will exclude the HCP Process. The details of the analyses are in Section 10.3.1, Section 10.3.2, and Section 10.3.3. If a patient is not covered by any of the analysis populations, but experiences an AE, this AE will be reported in a separate listing.

Observational AEs: SAEs, AEs of Special Interest and AEs that lead to permanent discontinuation of HUMIRA[®] occurring from the first day in the registry (enrollment visit or date of informed consent, through the last contact (as defined in Section 10.3.1) irrespective of drug treatment duration.

Registry Treatment-emergent AEs: SAEs, AEs of Special Interest and AEs that lead to permanent discontinuation of HUMIRA® occurring from the first recorded dose of HUMIRA® in the registry through 70 days after the last dose excluding AEs occurring during treatment interruptions (as defined in Section 10.1).

All Treatment Emergent AEs: SAEs, AEs of Special Interest and AEs that lead to permanent discontinuation of HUMIRA® occurring from the first recorded dose of HUMIRA® (initial dose) through 70 days after the last dose excluding AEs occurring during treatment interruptions (as defined in Section 10.1.

AEs for intermittent treatment: SAEs, AEs of Special Interest and AEs that lead to permanent discontinuation of HUMIRA® in the Intermittent Treatment Population.

Observational AEs excluding HCP process: SAEs, AEs of Special Interest and AEs that lead to permanent discontinuation of HUMIRA® occurring from the first day in the registry through the last contact excluding the HCP process.

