10.3.1 Analysis of Observational AEs

The number and percent of patients experiencing SAEs, AEs of Special Interest and AEs that lead to permanent discontinuation of HUMIRA® during the registry, regardless of whether the AEs are reported during or after the HUMIRA® treatment, will be tabulated by body system and Medical Dictionary for Drug Regulatory Activities (MedDRA) preferred term. Rates (event per 100 patient-year of observation) of SAEs and AEs of Special Interest and the 95% confidence interval will be provided. The analysis will be performed using data from first day in the registry to the date of last contact for the All Treated Patient Population. The last contact date is defined as the last date of registry or direct to HCP process participation, whichever occurs later.

Standardized incidence ratios (SIRs) will be used to compare the rates of events in this registry to the general population.

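### Section 10.3.4 divides AEs that lead to permanent discontinuation by observation time that includes the years after stopping, so this one rate falls as stoppers are retained

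*Protocol*

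**What the plan says.** Protocol 10.3.4 specifies "Rates (event per 100 patient-year of observation) of SAEs, AEs of Special Interest and AEs that lead to permanent discontinuation of" HUMIRA, each with a 95% confidence interval. The analysis is run "using data from first day in the registry through the last contact, excluding the HCP process".

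That time does not stop with the drug. Section 10.2 states: "Duration of observation in the registry is defined from the first day in the registry". It runs on to the end of the registry without reference to treatment. Section 10.3 describes the observational AEs as collected "irrespective of drug treatment duration". Sections 6.4, 6.5, 6.6 and 7.4 ask physicians to keep patients who have stopped HUMIRA in the registry for the rest of the 10-year period, in the words of 6.4 "irrespective of future treatment decisions so that important and complete safety information can be obtained".

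Two neighbouring sections treat the category differently:

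- 10.3.1 counts AEs leading to permanent discontinuation (n and %), but limits its rates to the other two categories: "Rates (event per 100 patient-year of observation) of SAEs and AEs of Special Interest and the 95% confidence interval will be provided".
- 10.3.2 gives them a rate per 100 patient-years of exposure.

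Table 2 (7.1.2) contains two AESI categories that depend partly on stopping: "Hepatic events that are serious or lead to permanent discontinuation of HUMIRA" and "Hematologic events that are serious or lead to permanent discontinuation of HUMIRA".

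**The concern.** An AE can lead to permanent discontinuation only in a patient who has not yet permanently discontinued. After that point the numerator for the patient is closed, while each further registry year still enters the denominator. This holds for patients who stopped for any reason, including loss of effect or preference, and not only for those who stopped because of an AE.

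The rate therefore depends on how many stoppers are retained and for how long, as well as on tolerability. The protocol deliberately seeks good retention, and good retention lowers this rate without any change in the events. A reader who sets the 10.3.4 figure beside the 10.3.2 figure would see two quite different rates for largely the same events, and could take the lower one as a statement about tolerability.

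SAEs do not have this problem. They can occur off drug, so observation time is a legitimate denominator for them.

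**Working it through.** **Is there a stated figure to reproduce?** No. The protocol gives no count, rate or stopping hazard for this category. The only related figures are the planned person-years in 10.6, and they reproduce: 5,000 × 10 × (1 − 0.40) = 30,000 PY and 6,000 × 10 × 0.60 = 36,000 PY, or 6 PY per patient. Section 10.6 does not say whether these include HCP-process time, which 10.3.4 excludes, so they serve only as a scale.

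**Bias factor.** Let D be the number of AEs leading to permanent discontinuation, P the registry observation time (HCP process excluded), and f the share of P after permanent discontinuation.

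- Rate as in 10.3.4: D / P
- Rate over time at risk: D / [(1 − f) P]
- Ratio: 1 − f

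With f assumed at 0.3, 0.5 or 0.6, the 10.3.4 rate is 30%, 50% or 60% below the at-risk rate.

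**Illustration 1 (scale).** Inputs: 36,000 PY from 10.6; an assumed mean of 3 years on drug; an assumed 300 events.

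- Per observation: 300 / 36,000 = 0.83 per 100 PY
- Per time on drug: 300 / (6,000 × 3) = 300 / 18,000 = 1.67 per 100 PY

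Here f = 0.5.

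**Illustration 2 (retention alone).** All inputs are assumed: 5,000 patients, of whom 3,000 stop after 2 years (500 of them for an AE) and 2,000 stay on drug for 10 years. On-drug time is 3,000 × 2 + 2,000 × 10 = 26,000 PY, and 500 / 26,000 = 1.92 per 100 PY. Only the further registry follow-up of the 3,000 stoppers is varied:

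| Extra years per stopper | Observation PY | f | Rate per 100 PY of observation |
|---|---|---|---|
| 0 | 26,000 | 0 | 1.92 |
| 2 | 32,000 | 0.19 | 1.56 |
| 4 | 38,000 | 0.32 | 1.32 |
| 8 | 50,000 | 0.48 | 1.00 |

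The 500 events are the same in every row.

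**Illustration 3 (constant hazards, everyone followed for T years).** With AE-stop hazard λ and other-stop hazard μ, on-drug time per patient is E = [1 − exp(−(λ+μ)T)] / (λ+μ). The rate over E is λ at every T; the rate over T is λE/T. With λ assumed at 2.0 per 100 PY and μ at 0.05 to 0.15 per year, the observation rate falls from 1.93–1.84 at T = 1 to 1.44–0.96 at T = 10. With λ = 5.0 per 100 PY it falls from 4.76–4.53 to 3.16–2.16.

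**Table 2 categories.** Let q be the share of the properly based hepatic (or hematologic) AESI rate that comes from non-serious events qualifying only by leading to discontinuation. Serious events keep their full observation-year rate and the rest is multiplied by (1 − f), so the combined rate is understated by the fraction q × f. This lies between 0 (q = 0) and f (q = 1). The protocol gives neither q nor f. In 10.3.1, f must be taken over observation that includes HCP-process time.

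**The case against.** The strongest reply is that the appropriate rate is already planned. Section 10.3.2 gives these AEs per 100 patient-years of exposure, for both registry and all treatment-emergent events, and 10.3.3 does so for the Intermittent Treatment Population. The n (%) in 10.3.4 do not depend on the denominator, and the 10.3.4 rate is openly labelled as per observation time. All of this stands, and it limits the point to one reported rate. It does not make that rate useful, because a correctly based figure elsewhere is no reason to print a second one that moves with retention.

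Several stronger readings are tempting but are not supported:

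- *Stoppers are followed for 10 years after stopping.* The 10 years run from registry entry. A patient who stops at year 4 has at most 6 years left, and 10.3.4 leaves out HCP-process years.
- *The sections contradict each other.* Section 10.3 sets up five analyses with different windows, so observation and exposure denominators differ by design. The mismatch between 10.3.1 and 10.3.4 is one of scope: one omits the rate and the other includes it.
- *The observational AESI rates are biased low in general.* Serious hepatic and hematologic events qualify on or off drug. Only the non-serious events that qualify through stopping are affected.
- *The primary safety result is compromised.* Section 6.0 names SAEs and AESIs as the incidences and rates to be assessed; AEs leading to discontinuation are an additional collected category.

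A further fair objection is that the exposure denominator is not exact time at risk. Under 10.2 it ends 14 days after the last dose and excludes interruptions, while 10.3.2 counts events through 70 days after the last dose, a gap of 70 − 14 = 56 days. A patient in a temporary interruption can also have an AE that makes the stop permanent. This stands and shapes the fix.

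**Conclusion.** The point holds for the rate of AEs leading to permanent discontinuation in 10.3.4. It is understated by the fraction f relative to time at risk, and the direction is certain whenever any patient is followed in the registry after stopping permanently. The size is unknown because the protocol does not give f. The halving in the illustrations rests on assumed stopping patterns and event counts and is not a forecast.

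The consequence is one potentially misleading secondary figure. The counts and percentages, the SAE rates and the exposure-based rate in 10.3.2 are not touched by this dilution. The hepatic and hematologic AESI rates in 10.3.1 and 10.3.4 are affected only through their non-serious, discontinuation-defined part, by q × f, which is a minor issue of unknown size. The change is worth making because it is cheap and brings 10.3.4 into line with 10.3.1.

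**What to change.** In 10.3.4, remove AEs that lead to permanent discontinuation from the rates per 100 patient-years of observation, as 10.3.1 already does. Keep their n (%) and refer the reader to the rate in 10.3.2.

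If a rate is wanted within 10.3.4, compute it over registry time from the first registry dose to permanent discontinuation (or last registry contact if the patient has not stopped). Include temporary interruptions, and count events over exactly the same window. Borrowing the 10.2 exposure definition unchanged would carry over the 14-day versus 70-day mismatch.

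State explicitly that observation time for 10.3.4 ends at the last registry contact, because 10.2 refers to an end-of-registry that Section 12.0 ties to the last registry or HCP visit.

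Optionally, in 10.3.1 and 10.3.4, show serious hepatic and hematologic AESIs (observation-year rate) separately from non-serious ones that qualify only through discontinuation (n and %, or a rate up to discontinuation).

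The cost is a wording change in 10.3.4 and, if adopted, one extra split in two AESI categories. No new data are needed, since dosing, event details and action taken are already collected.
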